13.0 Version History

Table 4.SAP Version History Summary

[figure not shown]
Version	Date	Summary		
1.0	27 Mar 2018	Initial version		
2.0 - Draft	07 Aug 2023	Adopted the latest SAP template.		
		 Added language for estimands in Section 2.1 and intercurrent events handling in Section 8.0 for primary and multiplicity- controlled secondary endpoints. 		
		Updated analysis details according to the current study design and agency's responses since SAP v1.0, including:		
		 Updated Missing data handling approaches, with details of NRI-MI including seed, number of datasets, and how results will be combined in Section 9.2. 		
		Added details of multiplicity testing procedure for primary and secondary endpoints in Section 12.0.		
		O Updated key statistical analysis for primary and secondary endpoints in Section 9.0, including stratification factors used in all models, with MMRM replacing ANOVA/ANCOVA for secondary continuous endpoints, using van Elteren test for analyzing cumulative CS exposure, and including details about analysis of count and time-to-event endpoints.		
		o Included analysis plan for Period 2 endpoints in Section 9.5.		
		 Added tipping point analysis for the secondary continuous endpoints in Section 9.4.3 and Appendix F. 		
		 Added additional as observed analysis for secondary endpoints including primary endpoint components in Section 9.2 and Section 9.4.3. 		
		Updated safety analysis including:		
		 Added SS LT in Section 4.0. 		
		 Including treatment as a fixed factor in ANOVA for safety variables in Section 10.3 and Section 10.4. 		
		 Included analysis for adverse event difference between each upadacitinib dose group and placebo group and corresponding forest plots for selected AESI in Section 10.2. 		
		 Included exposure-adjusted incidence rate for selected AESIs in Section 10.2.6. 		
		 Included cumulative incidence plots for AESIs in Section 10.2.6. 		

[figure not shown]
Version	Date	Summary
2.0	14 Feb 2024	 Updated estimands in Section 2.1. Added Race to Baseline disease characteristics in Section 7.1 Updated intercurrent events and intercurrent events handling in Section 8.0 and Section 9.4.
		 Updated missing data handling in Section 9.2.
		• Updated analysis for the endpoint of proportion of subjects who experience at least one disease flare through Week 52.
		Add ANCOVA analysis as additional analysis for continuous endpoint except for cumulative CS exposure
		 Add tipping point analyses as sensitivity analysis for the endpoint of cumulative CS exposure and proportion of subjects who experience at least one disease flare in Section 9.4.3.
		• Add summary for GCA signs and symptoms in Section 9.5.
		• Update list of AESI to align with the protocol and product safety statistical analysis plan in Section 10.2.6 and Appendix B.
		 Add analysis for treatment-emergent bone fracture and retinal detachment in Section 10.2 and Section 10.6.
		 Added sample code for NRI-MI in Appendix G and updated sample code for tipping point analysis in Appendix F.
		Updated seeds in Appendix H.

Appendix B. Definition of Adverse Events of Special Interest

Adverse Events of Special Interest (AESIs) will be identified using the following search criteria:

AESI	Type of MedDRA Query	Broad or Narrow Search	Search Criteria
Serious Infections	CMQ		"Infections" – Subset for SAEs
Opportunistic Infection excluding Tuberculosis and Herpes Zoster	CMQ		"Opportunistic infection excl. TB and Herpes Zoster"
Herpes Zoster	CMQ		"Herpes Zoster"
Active Tuberculosis	CMQ		"Active Tuberculosis"
Malignancy	SMQ	Narrow	"Malignant tumours"
Non-Melanoma Skin Cancer (NMSC)	SMQ	Narrow	Skin Malignant tumours (Narrow SMQ) removing Melanoma CMQ
Malignancy excluding NMSC			"Malignant tumours" SMQ (Narrow SMQ) removing NMSC output
Lymphoma	SMQ	Broad	"Malignant Lymphomas"
Adjudicated Gastrointestinal Perforations			"Gastrointestinal Perforation" Events will be based on medical review and adjudication (the identification of events to be adjudicated are described in the GI Perforation charter)
Anemia	CMQ		"Non-Hemolytic and Non- Aplastic Anemias"
Neutropenia	CMQ		"Hematological Toxicity – Neutropenia"
Lymphopenia	CMQ		"Hematological Toxicity — Lymphopenia (Upadacitinib Product Specific)"
Renal Dysfunction	SMQ	Narrow	"Acute Renal Failure"
Hepatic Disorder	SMQ	Narrow	"Drug Related Hepatic Disorders – Comprehensive Search SMQ"
Creatine Phosphokinase (CPK) Elevation	PT		PT of "Blood creatine phosphokinase increased"

AESI	Type of MedDRA Query	Broad or Narrow Search	Search Criteria
Adjudicated MACE*	Output from CAC		Based on adjudicated results (the identification of events to be adjudicated are described in the CAC Charter)
Adjudicated Venous Thromboembolic Events**	Output from CAC		Based on adjudicated results (the identification of events to be adjudicated are described in the CAC Charter)
Adjudicated Arterial Thromboembolic Events	Output from CAC		Based on adjudicated results (the identification of events to be adjudicated are described in the CAC Charter)

^{*} MACE; Major Adverse Cardiovascular Events, defined as cardiovascular death, non fatal myocardial infarction and non fatal stroke. In addition, undetermined/unknown cause of deaths and other cardiovascular events from CAC will be summarized.

In addition to AESIs listed above, adverse events of bone fracture and retinal detachment will be identified using the following search criteria:

Adverse Events	Type of MedDRA Query	Broad or Narrow Search	Search Criteria
Bone Fracture	CMQ	"Bone fractures"	
Retinal Detachment	CMQ	"Retinal Detachment (Upadacitinib Product Specific)"	

^{**} Venous thromboembolic events (VTE) include deep vein thrombosis (DVT) and pulmonary embolism (PE), and PE/DVT (fatal and non fatal).

Appendix C. Potentially Clinically Important Criteria for Safety Endpoints

The criteria for Potentially Clinically Important (PCI) laboratory findings are described in Table C-1 and Table C-2, and the PCI criteria for vital sign findings are described in Table C-3.

Table C-1. Criteria for Potentially Clinically Important Hematology Values

		Definition of Potentially Clinically Important	
Hematology Variables	Units	Very Low	
Hemoglobin	G/L	< 80	
Leukocytes	10 ⁹ /L	< 2.0	
Lymphocytes	10 ⁹ /L	< 0.5	
Neutrophils	10 ⁹ /L	< 1.0	
Platelets	10 ⁹ /L	< 50	

Note: A post baseline grade must be more extreme than the baseline grade to be considered a potentially clinically important finding.

[figure not shown]
Table C-2. Criteria for Potentially Clinically Important Chemistry Values

		Definition of Potentially Clinically Important		
Chemistry Variables	Units	Very Low	Very High	
ALP	U/L		> 5.0 × ULN	
SGOT/AST	U/L		> 5.0 × ULN	
SGPT/ALT	U/L		> 5.0 × ULN	
Total Bilirubin	umol/L		> 3.0 × ULN	
Albumin	g/L	< 20		
Glucose (fasting)	mmol/L	< 2.2	> 13.9	
Creatinine	mcmol/L		> 3.0 × ULN	
Potassium	mmol/L	< 3.0	> 6.0	
Corrected Calcium	mmol/L	< 1.75	> 3.1	
Sodium	mmol/L	< 130	> 155	
Phosphate	mmol/L	< 0.6		
Creatine Kinase (CPK)	U/L		> 5.0 × ULN	
Total Cholesterol	mmol/L		> 10.34	
Triglycerides	mmol/L		> 5.7	
Urate	umol/L		> 590	

Note: A post baseline grade must be more extreme than the baseline grade to be considered a potentially clinically important finding.

Table C-3. Criteria for Potentially Clinically Important Vital Sign Values

Vital Signs Variables	Criterion	Definition of Potentially Clinically Important
Systolic Blood Pressure	Low	Value \leq 90 mmHg and decrease \geq 20 mmHg from Baseline
(mmHg)	High	Value ≥ 160 mmHg and increase ≥ 20 mmHg from Baseline
Diastolic Blood Pressure	Low	Value \leq 50 mmHg and decrease \geq 10 mmHg from Baseline
(mmHg)	High	Value ≥ 100 mmHg and increase ≥ 10 mmHg from Baseline
Pulse (bpm) Low		Value \leq 50 bpm and decrease \geq 15 bpm from Baseline
	High	Value ≥ 120 bpm and increase ≥ 15 bpm from Baseline
Weight	Low	> 7% decrease from Baseline
	High	> 7% increase from Baseline

Appendix D. National Cholesterol Education Program (NCEP) Adult Treatment Panel III (ATP III) for Selected Lipid Parameters

- LDL cholesterol ($< 3.36, \ge 3.36 \text{ and } < 4.14, \ge 4.14 \text{ mmol/L}$)
- HDL cholesterol ($< 1.03, \ge 1.03 \text{ mmol/L}$)
- Total cholesterol ($< 5.17, \ge 5.17$ and $< 6.21, \ge 6.21$ mmol/L)
- Triglycerides (< 1.69, \geq 1.69 and < 2.26, \geq 2.26 mmol/L)

Appendix E. Interim Futility Analysis Based on the Conditional Power

Let parameters P_1 and P_0 represent the sustained remission response rates at Week 24 for upadacitinib 15mg dose group and the placebo group respectively and let n and n/2 be the sample size in each group. Let α denote the type 1 error rate and β denote the type 2 error rate (so $1 - \beta$ is the test power). The null and alternative hypotheses have the form:

$$H_0: P_1 - P_0 = 0$$
 vs. $H_1: P_1 - P_0 > 0$.

[figure not shown]
The test statistic has the following form:

$$Z = \frac{\hat{P}_1 - \hat{P}_0}{\sqrt{\frac{\hat{P}_1(1 - \hat{P}_1)}{n} + \frac{\hat{P}_0(1 - \hat{P}_0)}{n/2}}},$$

where \hat{P}_1 and \hat{P}_0 are the sample response rates for the 15mg dose group and the placebo group respectively. The null hypothesis is rejected at a two-sided α level if $Z>Z_{\alpha/2}$, where $Z_{\alpha/2}$ is the upper $\alpha/2$ percentile of the standard normal distribution.

Let m=70 and m/2=35 denote the sample size in upadacitinib 15 mg group and placebo group at the interim futility analysis. Let $Z^{(m)}$ denote the test statistic at the interim futility analysis (for the comparison of 15 mg dose group vs. placebo), and let $Z^{(n)}$ denote the corresponding test statistic at the final analysis. Let $t=\frac{m}{n}$ denote the information fraction at the interim futility analysis (t=1/3). Given that we observe at the interim

[figure not shown]
$$Z^{(m)} = z = \frac{\hat{P}_{1,m} - \hat{P}_{0,m/2}}{\sqrt{\frac{\hat{P}_{1,m}(1 - \hat{P}_{1,m})}{m} + \frac{\hat{P}_{0,m/2}(1 - \hat{P}_{0,m/2})}{m/2}}},$$

where $\hat{P}_{1,m}$ and $\hat{P}_{0,m/2}$ are the sample response rates at the interim analysis for 15 mg and placebo groups respectively. The conditional power under the current trend is calculated as:

$$CP(t,z) = Prob(Z^{(n)} > Z_{\alpha/2} | Z^{(m)} = z \,) = \Phi\left(\frac{z}{\sqrt{t(1-t)}} - \frac{Z_{\alpha/2}}{\sqrt{1-t}}\right),$$

where $Z_{\alpha/2}$ is the upper $\alpha/2$ percentile of the standard normal distribution. The conditional power will be compared with the futility boundary 0.15. The whole trial is to be terminated if CP(t, z) < 0.15.

Appendix F. Tipping Point Analysis for Secondary Continuous Endpoints (except for cumulative CS exposure)

To assess the impact of potential departures from the missing at random assumption, tipping point analyses are conducted as a sensitivity check for change from Baseline in the multiplicity-controlled secondary continuous endpoints at Week 52.

The tipping point analyses are two-dimensional, i.e., assumptions about the missing outcomes on the upadacitinib treatment groups and the placebo group can vary independently. In addition, the focus is on scenarios where missing outcomes on upadacitinib are worse than the imputed values on upadacitinib, while missing outcomes on placebo are better than the imputed values on placebo, for the visit of interest. Missing values are first imputed via MI under MAR assumption using data before ICEs at all visits, and then a shift parameter is applied to the imputed values of the visit of interest (a different shift parameter may be specified for each treatment group). This is implemented by PROC MI using the MNAR statement. The number of imputed datasets is 30.

More specifically, PROC MI using the sequential fully conditional specification (FCS) method⁵ will be performed to impute any missing value and does not rely on a monotone missing pattern. It also can achieve the exact shifted values for tipping point analysis. Treatment is included in the FCS imputation model to enable sampling conditional on treatment groups. Additionally, the imputation model includes the same stratification factors that are used in the primary analysis and the Baseline value of the endpoints of interest, as well as longitudinal response observed at any other prior visits.

For a given pair of shift parameters, the SAS code example is as follows. Prior to the code below, any missing Baseline categorical variables are singly imputed with the most common level of each variable. Any missing baseline continuous variables are handled with FCS based on other baseline variables. Assessment at Baseline was not collected for TSQM. Thus, consideration for Baseline in the model is not applicable for TSQM.

```
PROC MI DATA=DATA WIDE OUT=DATA WIDE BOUNDED NIMPUTE=30
SEED=12345;
   CLASS TRTP &COVCAT;
   VAR trtp &COVCON &COVCAT WEEK 8 WEEK 12 WEEK 24 WEEK 52;
   /* FCS for baseline continuous variables */
   FCS reg(base = trtp &COVCAT);
   /* Sequential FCS for endpoint at different visits */
   FCS reg(WEEK 8 = trtp &COVCAT &COVCON);
   FCS reg(WEEK 12 = trtp &COVCAT &COVCON WEEK 8);
   FCS reg(WEEK 24 = trtp &COVCAT &COVCON WEEK 8 WEEK 12);
   FCS reg(WEEK 52 = trtp &COVCAT &COVCON WEEK 8 WEEK 12
   WEEK 24);
  MNAR ADJUST (WEEK 52 / SHIFT=&SJ1
   ADJUSTOBS=(TRTP='PLACEBO'));
  MNAR ADJUST (WEEK 52 / SHIFT=&SJ2 ADJUSTOBS=(TRTP='UPA
   7.5MG'));
  MNAR ADJUST (WEEK 52 / SHIFT=&SJ2 ADJUSTOBS=(TRTP='UPA
   15MG'));
RUN;
```

Note: The input dataset is in wide format. TRTP denotes the treatment group. &COVCON denotes baseline continuous covariates including baseline value of the endpoint of interest. &COVCAT denotes categorical covariates including the stratification factors (baseline CS dose [prednisone or prednisolone > 30 mg or ≤ 30 mg], and entering study with new onset or relapsing disease). WEEK 8, WEEK 12, WEEK 24, WEEK 52 denote the observed values at each visit. &SJ1and &SJ2 denote the shift parameters for the placebo group and upadacitinib groups respectively.

In cases where the shifted values are smaller than the minimum or larger than the maximum value of the endpoint, (i.e., out of range), the minimum or maximum value of the endpoint is used in further analysis steps.

For each pair of shift parameters, the SAS procedure PROC MIXED is used for the ANCOVA model which includes the fixed effects of treatment, stratification factors (Baseline CS dose [prednisone or prednisolone > 30 mg, prednisone or prednisolone ≤ 30 mg], and Baseline disease status [new onset disease, relapsing disease]), and the continuous fixed covariate of Baseline measurement on each of the imputed datasets to obtain the results for each upadacitinib treatment group versus the placebo group comparison. These results will be aggregated using Rubin's method to get p-values.

If one pair of shift parameters are found to just reverse the study conclusion, in terms of p-value larger than 0.05, then the shift parameters are identified as the tipping point. The results for a grid of shift parameter combinations are provided in tabular format.

The SAS code example of the data imputation step for tipping point analysis using MI is provided above. The SAS code example for the analysis and results combination step using PROC MIXED and PROC MIANALYZE at Week 52 is as follows, resulting in a treatment effect vs placebo for each upadacitinib group:

```
PROC MIXED DATA=ALL EMPIRICAL;
    ODS OUTPUT LSMEANS=MIXEDLSMEANS DIFFS=DIFF;
    BY Shift1 Shift2 IMPUTATION;
    CLASS TRTP AVISITN STRATA USUBJID;
   MODEL CHG = BASELINE TRTP AVISITN TRTP*AVISITN STRATA / SOLUTION;
    LSMEANS TRTP*AVISITN / CL PDIFF DIFF;
    REPEATED / subject = USUBJID;
RUN;
DATA DIFF1;
    SET DIFF;
    IF TRTP = 'PLACEBO' and avisitn = 52 and avisitn = 52;
    KEEP imputation shift1 shift2 trtp estimate stderr;
RUN:
PROC SORT DATA=DIFF1; BY Shift1 Shift2 trtp IMPUTATION ; RUN;
PROC MIANALYZE DATA=DIFF1;
    ODS OUTPUT PARAMETERESTIMATES=GROUP OUTPUT;
    BY shift1 shift2 trtp;
   MODELEFFECTS ESTIMATE;
    STDERR STDERR;
RUN;
```

Note: The input dataset ALL includes all (# of shift1 parameters) * (# of shift2 parameters) * (# of imputations in MI) imputed datasets. TRTP denotes the treatment group and STRATA denotes the stratification factors used in analysis. CHG denotes the change from baseline value and BASELINE denotes the baseline value.

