7.3 Statistical Analyses for Efficacy

Analysis of Primary and Key Secondary Endpoints in Period 1

For the global analysis, the overall type I error rate of the primary and ranked key secondary endpoints for the 2 upadacitinib doses will be strongly controlled using a graphical multiple testing procedure.

Specifically, the testing will utilize the endpoint sequence of primary endpoint followed by key secondary endpoints in the order as specified in Section 3.2 and Section 3.3. The testing will start with the primary endpoint of 15 mg QD with α = 0.05. Continued testing will follow a pre-specified α transfer path, which includes downstream transfer along the endpoint sequence within each dose as well as cross-dose transfer. The testing of 7.5 mg QD dose will start with transferred α if endpoint 7 in Section 3.3 of the 15 mg QD dose is significant. The group of endpoints labeled as 8 in Section 3.3 will be tested using the Hochberg procedure, conditional on significance of higher ranked endpoints. More details of the graphical procedure will be specified in the SAP. An alternative testing procedure will be done for the regulatory purposes in Japan. More details of the graphical procedure will be specified in the SAP. Unless otherwise specified, all statistical tests will be performed at a 2-sided significance level of 0.05.

The primary analysis will be conducted after all subjects have completed the Week 52 visit or have prematurely discontinued from the study prior to Week 52. For the primary efficacy endpoint, the upadacitinib groups will be compared with the PBO group using the Cochran-Mantel-Haenszel method adjusting for stratification factors. The primary approach for handling missing data will be Non-Responder Imputation incorporating multiple imputation (NRI-MI). Subjects with missing data will be counted as non-responders, except when missing at random can be reasonably assumed, which will be handled by multiple imputation. For example, missing due to COVID-19 logistical restriction or due to political conflict will be handled by multiple imputation. A sensitivity analysis will be performed based on As Observed analysis in which subjects with missing components of sustained remission at Week 52 will be excluded from analysis. Other key binary endpoints will be analyzed similarly.

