12.0 Overall Type-I Error Control

The overall Type I error rate of the primary and the multiplicity-controlled secondary endpoints will be strongly controlled using a graphical multiplicity adjustment method.^{3,4}

Specifically, the primary and multiplicity-controlled secondary endpoints as specified in Section 3.1 and Section 3.2 will be tested in the order as specified below and will begin with testing the primary endpoint for upadacitinib 15 mg dose using α of 0.05. Continued testing will follow a pre-specified α transfer path which includes downstream transfer along the endpoint sequence within each dose as well as cross-dose transfer. Adjusted P values for the primary and multiplicity-controlled secondary endpoints will be provided based on the testing procedure.

The testing procedures are provided below in Figure 2 (for US/FDA regulatory purpose) and Figure 3 (for PMDA regulatory purpose). The arrows specify the α transfer paths. Once a null hypothesis of an endpoint is rejected (i.e., deemed significant) at its assigned significance level, its significance level will be transferred to subsequent endpoint(s) following the arrow(s). The numbers on the arrows denote the weights for transferring and (possibly) splitting significance levels. Specifically, the weight 1 and 1/2 denotes 100% and 50% transfer of significance level, respectively. The primary and multiplicity-controlled secondary endpoints (V1-V7 in Table 3) will be tested sequentially. The remaining multiplicity-controlled secondary endpoints will be grouped together (V8-H in Table 3) and tested using Hochberg procedure.

[figure not shown]

Table 3. List of Primary and Secondary Endpoints for Regulatory Purpose (FAS1)

Name	Variable			
V0	Proportion of subjects achieving sustained remission at Week 52			
V1	Proportion of subjects achieving sustained complete remission from Week 12 through Week 52			
V2	Cumulative CS exposure through Week 52			
V3	Time to first disease flare through Week 52			
V4	Proportion of subjects who experience at least 1 disease flare through Week 52			
V5	Proportion of subjects in complete remission at Week 52			
V6	Proportion of subjects in complete remission at Week 24			
V7	Change from Baseline in the 36-item Short Form Quality of Life Questionnaire (SF-36) Physical Component Score (PCS) at Week 52			

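### Appendix F judges every tipping point at an unadjusted p of 0.05, although FACIT-Fatigue, TSQM and the 7.5 mg comparisons may be decided at lower levels, so robustness could be overstated

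*SAP*

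**What the plan says.** SAP Appendix F covers the "multiplicity-controlled secondary continuous endpoints at Week 52", other than cumulative CS exposure. Appendix H, part C, lists them as SF-36 PCS, FACIT-Fatigue and TSQM global satisfaction. For each pair of shifts, the ANCOVA results from the 30 imputed datasets are pooled: "These results will be aggregated using Rubin's method to get p-values". A pair that only just overturns the study conclusion, "in terms of p-value larger than 0.05", is named the tipping point. The rule is the same for every endpoint and both doses, and the results for the whole grid of shifts are tabulated.

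SAP Section 12 sets out how the study conclusion is reached. Testing "will begin with testing the primary endpoint for upadacitinib 15 mg dose using α of 0.05". It then runs down a fixed order ("The primary and multiplicity-controlled secondary endpoints (V1-V7 in Table 3) will be tested sequentially"), and SF-36 PCS is V7. FACIT-Fatigue and TSQM sit in the next group, V8-H, with flare count and CS-related AEs. Protocol 7.3 says this group "will be tested using the Hochberg procedure, conditional on significance of higher ranked endpoints". On transfers, Section 12 says "the weight 1 and 1/2 denotes 100% and 50% transfer of significance level, respectively". For the lower dose, Protocol 7.3 says "The testing of 7.5 mg QD dose will start with transferred α if endpoint 7 in Section 3.3" is significant at 15 mg. Section 12 also promises adjusted p-values; Appendix F does not mention them.

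**The concern.** Appendix F states the right aim, which is to find the shift that overturns the conclusion, but measures it with a yardstick that Section 12 does not use throughout. A claim won at a level below 0.05 is lost as soon as p passes that level. Appendix F would go on counting it as intact until p passed 0.05. Where the two differ, the difference always favours the product: the named tipping point lies further from the missing-at-random result than the point at which the claim is lost. At stake is how convincing the robustness statement is for up to five of the six comparisons.

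**Working it through.** The plan gives no figure of its own on this point. Its one recomputable design figure, power of at least 90% for 60% against 40% with 210 and 105 subjects, reproduces (exact Fisher power 91.0%) and does not enter below.

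**1. Scope.** Three endpoints times two doses gives six comparisons.

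**2. SF-36 PCS at 15 mg.** All of the 0.05 starts on the 15 mg primary endpoint. Protocol 7.3 opens the 7.5 mg tests only after 15 mg endpoint 7, so nothing leaves the sequence earlier. The local level is 0.05 and Appendix F is correct here.

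**3. After 15 mg SF-36 PCS.** Two routes leave this node: downstream to the 15 mg V8 group, and across to 7.5 mg. The weights leaving a node cannot sum to more than 1, and the only weights named are 1 and 1/2. An equal split is the natural reading: 0.05 × 1/2 = 0.025 on each route. This is an assumption, because the arrows are in figures not shown. On it, five of the six comparisons start below 0.05, before any recycling.

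**4. Levels inside the Hochberg group.** The k-th largest of the four p-values is compared with (group level)/k. The procedure steps up: once one p-value passes, all smaller ones pass too.

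| Group level | k = 1 | k = 2 | k = 3 | k = 4 |
|---|---|---|---|---|
| 0.05 | 0.05 | 0.025 | 0.0167 | 0.0125 |
| critical z | 1.960 | 2.241 | 2.394 | 2.498 |
| 0.025 | 0.025 | 0.0125 | 0.0083 | 0.00625 |
| critical z | 2.241 | 2.498 | 2.638 | 2.734 |

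**5. What the fixed rule misses.** Suppose a shift moves FACIT-Fatigue from p = 0.004 to p = 0.03.
- Group level 0.025: no rank allows a p-value above 0.025, so the claim is lost. Appendix F does not flag it. The same holds for every p between 0.025 and 0.05.
- Group level 0.05, all four p-values at or below 0.05: all four are rejected. The claim stands and Appendix F is right.
- Group level 0.05, one other p-value above 0.05: 0.03 must now meet 0.025 or less. The claim is lost and is not flagged.

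**6. Size, by illustration.** Assume a main-analysis z of 3.0 or 3.5. The tolerated loss of z is the assumed z minus the critical z. The bracket gives the loss tolerated at 0.05 divided by the loss tolerated at the level in that row, from unrounded values.

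| Level | z = 3.0 | z = 3.5 |
|---|---|---|
| 0.05 | 1.04 | 1.54 |
| 0.025 | 0.76 (1.37) | 1.26 (1.22) |
| 0.0125 | 0.50 (2.07) | 1.00 (1.54) |
| 0.00625 | 0.27 (3.92) | 0.77 (2.01) |

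The overstatement is modest at 0.025 and large only at the lowest Hochberg rank with a weak starting result.

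**The case against.** The case for leaving the text alone has five parts.

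- **The levels are not visible.** The arrow weights are in Figures 2 and 3. Alpha might be recycled to restore 0.05 after one dose succeeds. This stands: the levels in the working are conditional.
- **Hochberg thresholds are not fixed per endpoint.** At a group level of 0.05 with all four endpoints successful, 0.05 is exactly the right cut-off. This also stands. A reader might infer that p = 0.03 always loses the claim, and that does not follow.
- **Nothing is hidden.** A reader might infer that lost claims will be reported as robust. The SAP does not say so: it applies no such label, and it tabulates the grid. If p-values are shown, anyone can apply another level. The named tipping point would still be misplaced.
- **A nominal 0.05 is a legitimate reference.** Protocol 7.3 sets two-sided 0.05 as the default level unless otherwise specified, and this is a sensitivity analysis. This does not rescue the rule. Section 12 does specify otherwise for these endpoints, and Appendix F ties its cut-off to the study conclusion rather than to nominal significance.
- **There are two graphs**, one for US/FDA and one for PMDA, so an endpoint may have two local levels. This stands, and the remedy must name the graph.

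**Conclusion.** The rule in Appendix F does not do what it says it does, except where the local level happens to be 0.05. It is right for SF-36 PCS at 15 mg under the sequence described in Protocol 7.3. For the other five comparisons the level may be below 0.05. On an assumed half split with no recycling it is 0.025 or lower, and the unflagged band runs from the local level up to 0.05. With a full 0.05 at the group, the band appears only when another group member fails.

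The finding is that robustness could be overstated. A reader might go further and conclude that most of these endpoints are certainly tested below 0.05. The text makes a split likely but does not show it. Nor is there any inflation of type I error in the main tests, because the tipping-point analysis does not feed into them. This is a minor point that is cheap to put right.

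**What to change.** In Appendix F, replace the fixed cut-off. Define the tipping point as the first shift pair at which the endpoint's multiplicity-adjusted p-value exceeds 0.05. Obtain it by re-running the Section 12 procedure for that pair, with the other endpoints' p-values held at their main-analysis values. Equivalently, it is the first pair at which the endpoint is no longer rejected at its local level.

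Name the graph used: Figure 2, with Figure 3 for the PMDA submission. Show the p-values in the grid, and keep nominal 0.05 as a reference contour only.

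The cost is about a sentence of SAP text and a re-run of the graph for each shift pair. Section 12 already commits to adjusted p-values, so no new method is needed. Two consequences should be accepted openly: tipping points may look slightly less favourable, and those for FACIT-Fatigue and TSQM will depend on the other p-values in their group, as the claims themselves do.
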